8.4.2 Further data of interest in group B (Plexa)

- Handling of the lead

The physician will evaluate the handling of the lead during the implantation procedure and document the results in a Plexa handling eCRF

- Lead measurements (RV pacing threshold, sensing amplitude, shock impedance, lead impedance)

Lead measurements of the RV lead will be performed during each follow-up. Mean values will be calculated from all patients for each type of measurement.

- RV Lead measurements at implantation with PSA

Measurements of the RV lead will be done during implantation with an pacing sensing analyzer (PSA). Data will be documented and mean values from all patients will be calculated for each type of measurement.

- Evaluation of sensing performance in the atrial channel

The sensing performance of Plexa DX leads will be evaluated by the physician for the atrial channel. Mean value will be determined.

- Percentage of DX leads among leads, atrial sensing amplitude in DX leads

Data of DX leads will be collected, including the percentage of used DX leads in ICD and CRT-D therapy. Furthermore the atrial sensing amplitude of DX leads will be collected and the mean values evaluated at 3- and 6-month follow-up.

- IEGMs of all episodes

All IEGMs of all medical episodes (excluding episodes based on technical triggers) will be collected for possible further evaluation.

- Home Monitoring data

Pseudonymized Home Monitoring data will be collected throughout study duration for potential further evaluations of continuously available device data.

- Adverse Events / Device Deficiencies

All AEs and DDs will be collected during the course of the study in a descriptive manner.

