8.4.1 Further data of interest in group A (Ilivia ICD family)

- MPP settings

The MPP settings used by the physicians will be collected for all CRT-D patients programmed to MPP "on". This includes the programmed vectors, the pacing threshold, the programmed pacing amplitudes, the LV sensing polarity, the sensing amplitude, the LV-LV and RV-LV delay as well as any change of setting during the course of the study.

- Handling of MPP programming (interface programmer)

The physician is asked to evaluate the handling of the MPP programming in an eCRF "MPP handling".

- SADE related to MPP during 6 months

SADEs which are possibly or securely related to MPP will be listed in a descriptive manner.

- Rate of responders/ non-responders to CRT therapy

These data will be collected from all patients implanted with a CRT-D device of the Ilivia family. The physician should evaluate at the 6-month follow-up if the respective patient is a responder or a non-responder to CRT-D therapy. Patients who did not tolerate MPP and had to be reprogrammed to MPP "off" during the course of the study contribute to the MPP "off" group.

- NYHA class, change of NYHA class in CRT-Ds

The NYHA class will be collected at baseline from all patients and at 6-month follow-up for CRT-D patients only. The mean change of NYHA class in CRT-D patients between enrollment and 6-month follow-up will be evaluated.

- Percentage of DX devices among devices, DX in CRT, atrial sensing amplitude in DX devices

Data of DX devices will be collected, including the percentage of used DX devices in ICD and CRT-D therapy. Furthermore the atrial sensing amplitude of DX devices as well as CRT statistics will be collected and the mean values evaluated at 3- and 6-month follow-up.

- Ventricular therapy episodes

Ventricular therapy and therapy attempt episodes will be collected and documented in a tachyarrhythmia episode eCRF, IEGMs of the episodes will be collected.

- Programming of Early ATP one-shot

The number of programming of Early ATP one-shot will be documented for all patients with programming of ATP one-shot in the VF zone. Number of occurred Early ATP one-shot will be collected based on the documented ventricular tachycardia IEGM episodes.

- Lead measurements (sensing amplitude, pacing threshold, pacing impedance, shock impedance) via pacing sensing analyzer (PSA) during implantation

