5.5. Exclusion of data from confirmatory data analysis

CIP chapter 11.12 Exclusion of data from the confirmatory data analysis

If the patient has atrial fibrillation during the device based measurements, the P-wave amplitude and the atrial threshold are not included in the analysis. Protocol deviations in regard to the follow-up schedule will not result in an exclusion of data in the analysis but will be subject to query management.

If the patient has atrial fibrillation during the device based measurements, data are classified as „not measurable: no p-wave visible“ in the CRFs.

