10.2. Variables

Implantation / ICD/CRTD

Data file, identifier patient_display_id_full	Descriptive	Variable name	Variable label	Variable level	Nominal values
implantation_general_data	Yes	imp_category	Study implantation	nominal	De novo CRT-D / ICD implantation Upgrade from pacemaker [...] Upgrade from ICD [...] Exchange of ICD / CRT-D [...]
implantation_general_data	Yes	imp_site	Implantation site	nominal	left / right
implantation_general_data	Yes	imp_dev_type_other	Device type	nominal	Single chamber ICD Dual Chamber ICD CRT-D
implantation_general_data	Yes	imp_dev	Device model	nominal	Ilivia 7 [...]
implantation_general_data	Yes	imp_dev_type	Device type	nominal	VR-T [...]
implantation_general_data	Yes	imp_connector	Connector type for RV lead	nominal	DF-1 / DF4

Implantation / Leads

Data file, identifier patient_display_id_full	Descriptive	Variable name	Variable label	Variable level	Nominal values
implantation_general_data	No	imp_rv_model	RV lead model	Nominal	Plexa S [...]
data_SAR	Yes	imp_rv_model_SAR ²⁴	RV lead model	Nominal	Plexa Other

²³ analysis_set_Ilivia_SAR = Yes

²⁴ IF imp_rv_model = Plexa S OR Plexa SD OR Plexa DF-1 S OR Plexa DF-1 SD or Plexa DF-1 S DX
THEN imp_rv_model_SAR = Plexa
ELSE imp_rv_model_SAR = other

Implantation Analyzer Data / RA

Data file, identifier_patient_display_id_full	Descriptive	Variable name	Variable label NEW prefix added to all labels "Implantation analyzer data, RA: "	Variable level	Nominal values
implantation_analyzer_data	Yes	imp_ana_ra_amp	Sensing amplitude [mV]	scale	n.a.
implantation_analyzer_data	Yes	imp_ana_ra_imp	Pacing impedance [Ω]	scale	n.a.
implantation_analyzer_data	Yes	imp_ana_ra_thresh	Pacing threshold [V] at Pulse width 0.4 ms	scale	n.a.
implantation_analyzer_data	No	imp_ana_ra_thresh2	Pacing threshold [V]	scale	n.a.
implantation_analyzer_data	No	imp_ana_ra_pulse	at Pulse width [ms]	scale	n.a.
data_SAR	Yes	imp_ana_ra_thresh_0 ⁵ ₂₅	Pacing threshold [V] at Pulse width 0.5 ms	scale	n.a.

A pacing threshold must always consist of amplitude and duration (pulse width). It is not reasonable to report one without the other.

Here, the CIP requires using 0.4 ms, but it can be expected that other pulse durations were used because different analyzer devices which are being used in the investigational centers have different standard settings.

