The CIP requires using 0.4 ms pulse width for all RA and RV threshold measurements. However, in the SAP version 1.0 it has been defined that it will be tested during blind review whether a meaningful number of measurements were performed with another pulse duration than 0.4 ms. This test showed that very few or no threshold measurements used other values than 0.4 ms at RA and RV measurements.

Therefore, **thresholds of device measurements will be reported for 0.4 ms pulse duration** only and measurements at other pulse duration will be discarded.

Implantation Device Data / RA / Not-measured

Data file, identifier patient_display_id_full	Descriptive	Variable name	Variable label	Variable level	Nominal values
implantation_device_data	No	imp_ra_amp_no	-	nominal	Not measurable: P-wave visible but [...] Not measurable: No P-wave visible Not done
data_SAR	Yes	imp_ra_amp_no_SAR ³⁹	Implantation device data, RA: Sensing amplitude	nominal	Not measurable: P-wave visible but Measured
implantation_device_data	No	imp_ra_imp_no	-	nominal	Out of range >3000 Out of range <200 Not measurable: no overpacing possible Not done
data_SAR	Yes	imp_ra_imp_no_SAR ⁴⁰	Implantation device data, RA: Pacing impedance	nominal	Out of range Measured
implantation_device_data	No	imp_ra_thresh_no	-	nominal	Not measured at 0.4 ms No capture with 7.5V possible Not measurable: no overpacing possible Not done
data_SAR	Yes	imp_ra_thresh_no_SAR ⁴¹	Implantation device data, RA: Pacing threshold	nominal	No capture with 7.5V possible Measured

³⁹ IF imp_ra_amp_no = Not measurable: P-wave visible but ... THEN imp_ra_amp_no_SAR = imp_ra_amp_no
ELSE IF imp_ra_amp ≠ missing THEN imp_ra_amp_no_SAR = Measured

⁴⁰ IF imp_ra_imp_no = Out of range >3000 OR Out of range <200
THEN imp_ra_imp_no_SAR = Out of range
ELSE IF imp_ra_imp ≠ missing THEN imp_ra_imp_no_SAR = Measured

⁴¹ IF imp_ra_thresh_no = No capture ... THEN imp_ra_thresh_no_SAR = imp_ra_thresh_no
ELSE IF imp_ra_thresh ≠ missing THEN imp_ra_thresh_no_SAR = Measured

Implantation Device Data / RV

Data file, identifier patient_display_id_full	Descriptive	Variable name	Variable label, NEW prefix added to all labels "Implantation device data, RV: "	Variable level	Nominal values
implantation_device_data	Yes	imp_rv_amp	Sensing amplitude [mV]	scale	n.a.
implantation_device_data	Yes	imp_rv_imp	Pacing impedance [Ω]	scale	n.a.
implantation_device_data	Yes	imp_rv_thresh	Pacing threshold [V] at Pulse width 0.4 ms	scale	n.a.

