13.2. Variables

3mFU General data

Data file, identifier patient_display_id_full	Descriptive	Variable name	Variable label, NEW prefix added to all labels "3mFU data: "	Variable level	Nominal values
fu_3_month_general_data	No	fu3_visdate	Date of 3-month follow-up	date	n.a.
fu_3_month_general_data	Yes	fu3_not_done	visit not performed	nominal	True / False
fu_3_month_general_data	Yes	fu3_interim	Did another follow-up occur since Pre-hospital discharge	nominal	Yes / No
fu_3_month_general_data	Yes	fu3_interim_reason	NEW: Reason for another FU	nominal	Home Monitoring alert Medical symptoms Other

The following variables are analyzed as defined for the Ilivia analysis set, as described in chapter 11.2.

3mFU Device Data / RA

3mFU Device Data / RA / Not-measured

3mFU Device Data / RV

3mFU Device Data / RV / Not-measured

3mFU Device Data / LV / Programmed Pacing Vectors

3mFU Device Data / LV / Programmed Pacing Vectors / Not-measured

3mFU Device Data / LV / Vector Change

3mFU Device Data / LV / Programmed Delay

3mFU Device Data / CRT / Atrial burden

3mFU Device Data / LV / Programmed Sensing Vector

Data file, identifier patient_display_id_full	Descriptive	Variable name	Variable label, NEW prefix added to all labels "3m FU data: "	Variable level	Nominal values
fu_3_month_device_data	Yes	fu3_lv_svect	Permanent programmed sensing vector	nominal	[...]
fu_3_month_device_data	Yes	fu3_lv_amp	Sensing amplitude [mV]	scale	n.a.

⁶⁶ analysis_set_Ilivia_SAR = Yes

3mFU Device Data / LV / Programmed Sensing Vector / Not-measured

Data file, identifier patient_display_id_full	Descriptive	Variable name	Variable label	Variable level	Nominal values
fu_3_month_device_data	No	fu3_lv_amp_no	-	nominal	No intrinsic rhythm Amplitude visible but too low to measure During intrinsic rhythm no R-wave visible Not done
data_SAR	Yes	fu3_lv_amp_no_SAR ⁶⁷	Implantation device data, any LV pacing vector: Sensing amplitude	nominal	Amplitude visible but too low to measure During intrinsic rhythm no R-wave visible Measured

3mFU Device Data / RA /System performance

Data file, identifier patient_display_id_full	Descriptive	Variable name	Variable label, NEW prefix added to all labels "3mFU data: "	Variable level	Nominal values
fu_3_month_device_data	No	fu3_perf_ra_sens	Adequate RA sensing	nominal	Yes / No
fu_3_month_device_data	Yes	fu3_perf_ra_sens_reason	Reason for inadequate RA sensing	nominal	Oversensing Undersensing Other

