21.2. Variables

The following variables are analyzed as defined for the Ilvia analysis set, as described in chapter 13.2.

3mFU General data

3mFU Device Data / RA (only Plexa DF-1 S DX)

3mFU Device Data / RA / Not-measured (only Plexa DF-1 S DX)

3mFU Device Data / RV

3mFU Device Data / RV / Not-measured

RV measurements will be reported for all Plexa leads, and for Plexa leads with DF4 connectors (see 19.2).

3mFU Device Data / RV/ System performance

Data file, identifier patient_display_id_full	Descriptive	Variable name	Variable label, NEW prefix added to all labels "3mFU data: "	Variable level	Nominal values
fu_3_month_device_data	Yes	fu3_perf_rv_sens	Adequate RV sensing	nominal	Yes / No
fu_3_month_device_data	Yes	fu3_perf_rv_sens_reason	Reason for inadequate RV sensing	nominal	Oversensing Undersensing Other
fu_3_month_device_data	Yes	fu3_perf_rv_pac	Adequate RV pacing	nominal	Yes / No
fu_3_month_device_data	Yes	fu3_perf_rv_pac_reason	Reason for inadequate RV pacing	nominal	Non-capture No output Other
fu_3_month_device_data	Yes	fu3_perf_rv_pac_nocap	NEW: Reason for non-capture RV	nominal	medical [...] technical

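### The SAP gives no adequacy rate for atrial sensing, pools DX with conventional atrial leads in group A, and sets a lost atrial signal to missing together with atrial fibrillation

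*Protocol*

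**What the plan says.** **What the CIP promises**

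- Group B (CIP 8.4.2): "The sensing performance of Plexa DX leads will be evaluated by the physician for the atrial channel", with a summary value to follow. Also: "Furthermore the atrial sensing amplitude of DX leads will be collected and the mean values evaluated at 3- and 6-month follow-up".
- Group A (CIP 8.4.1): an item headed "Percentage of DX devices among devices, DX in CRT, atrial sensing amplitude in DX devices". A separate item has the physician rate sensing and pacing in every available channel, summarised by lead type.
- CIP 8.5.11 requires the rating at month 3. In group B this means the RV channel and, for DX leads, atrial sensing as well.

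**What the SAP outputs**

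- SAP 13.2 (group A, month 3) lists `fu3_perf_ra_sens`, labelled "Adequate RA sensing", with Descriptive = No. The reasons for inadequate RA sensing are set to Yes.
- SAP 21.2 (group B, month 3) has one performance block, "3mFU Device Data / RV/ System performance". There is none for the RA.
- SAP chapters 10, 11, 13 and 14 summarise RA amplitude for the whole Ilivia analysis set. Footnote 24 reduces the RV lead model to Plexa or other ("THEN imp_rv_model_SAR = Plexa").
- SAP 5.5 states: "If the patient has atrial fibrillation during the device based measurements, data are classified as" not measurable because no P-wave is visible. Footnote 39 then reads "IF imp_ra_amp_no = Not measurable: P-wave visible but ... THEN imp_ra_amp_no_SAR = imp_ra_amp_no", and its only other outcome is Measured. Footnote 26 does the same for the analyzer data.

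**The concern.** Atrial sensing through the floating dipole is part of the intended use of the Plexa DF-1 S DX lead (CIP 4.5), and DX in CRT-D is a new feature of the Ilivia family. CIP 6.2.3 says that DX atrial sensing might be inferior to a standard atrial lead, and Table 8d lists this with unknown frequency. The study exists to evaluate residual risks of this kind.

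Followed as written, the SAP produces no rate of adequate atrial sensing. In group A it produces no amplitude specific to DX. Its one table on unmeasurable atrial signals cannot show the worst case, a dipole that gives no signal in a patient who is not in AF. What remains is conditional on a P-wave having been seen, so it leans towards good sensing.

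**Working it through.** The plan states no figure on this point, so there is none to reproduce. The check follows each output from the CIP to the SAP.

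**1. Adequacy rate.** The SAP Introduction defines Descriptive = No as data needed only to build derived variables. No derived variable in the SAP uses `fu3_perf_ra_sens`, so in group A the rating is collected and then not shown. RA pacing adequacy, in the same table, is set to Yes. Group B has no RA performance block. Month 6 cannot fill the gap, because CIP 9.6 leaves this evaluation out. Group A does tabulate reasons for inadequate RA sensing, which gives counts of rated failures but no rate and no DX split. The SAP list of reasons (oversensing, undersensing, other) also lacks the *not measurable* reason that CIP 8.5.11 provides.

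**2. Amplitude and DX use.** In group B the RA tables are restricted to Plexa DF-1 S DX at implantation, PHD, month 3 and month 6 (SAP 19.2, 20.2, 21.2, 22.2). That delivers the amplitude item of CIP 8.4.2.

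In group A there is no restriction. The planned mix (CIP 8.8.1) is 26 single-chamber, 26 dual-chamber and 53 CRT-D patients. If every patient with an atrial channel is measured, the DX share of the pooled mean can run from 0% (no DX system) to (26 + 53)/(26 + 53 + 26) = 79/105 = 75% (all single-chamber and all CRT-D patients DX). As an illustration with assumed counts, if 15 of 60 measured patients are DX and the dipole differs from conventional leads by 1 mV, the pooled mean moves by 1 × 15/60 = 0.25 mV.

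`imp_dev_type` is tabulated in group A, so VR-T DX use is visible. An HF-T QP device has the same type with or without a DX lead, and footnote 24 removes the lead model that would tell them apart.

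**3. Lost signal.** The footnotes treat the two chambers differently:

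| Record | RA (footnotes 26, 39) | RV (footnotes 30, 42) |
|---|---|---|
| Amplitude entered | Measured | Measured |
| Signal visible but not measurable | kept | kept |
| No signal visible | set to missing | kept as its own category |
| AF (RA) or no intrinsic rhythm (RV) | same code as the row above, missing | separate code, missing |
| Not done | missing | missing |

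CIP 11.12 excludes atrial measurements for AF only. The RA rule excludes every record with the shared code.

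The documents give no DX count, AF rate or loss rate, so the effect can only be illustrated. Assume 40 DX patients, 8 in AF, 4 not in AF with no atrial signal, and none in the visible-but-not-measurable category:

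- Measured: 40 − 8 − 4 = 28
- SAP output: 28/28 = 100%, with 12 missing
- Loss separated from AF: 28/(28 + 4) = 28/32 = 87.5%

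With assumed loss of 5% to 20% and AF of 0% or 20%, the SAP proportion stays at 100%, while the separated figure runs from about 95% down to about 75%.

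**The case against.** **Group B already reports DX amplitude.** This stands. A reader might infer that DX atrial sensing cannot be read from the SAP at all; the DX-only tables in chapters 19 to 22 rule that out. Those amplitudes exist only for patients with a measured P-wave, so they do not replace an adequacy rate.

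**The Descriptive = No flag may be a slip.** The same flag sits on RV and LV sensing adequacy in SAP 13.2, and on `fu3_perf_rv_sens` in SAP 24.2, which is a secondary endpoint with a test and confidence interval. A slip is plausible, but for the RV the result is rescued by chapters 21 and 24. For the RA nothing else reports it.

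**Nothing is deleted.** It is tempting to say that patients with a lost signal vanish. They are set to missing, and the standard tables in SAP 5.1 print a missing count. That count mixes AF, lost signal and measurement not done, so it does not show the loss.

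**Use of the shared code for a silent dipole is an inference.** Fair: the option labels are abbreviated and the eCRF instructions are not in the documents. But the RA list offers no other evident code for this case.

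**Not every such record outside AF is a lead failure.** This also stands. The RA list has no option for absent intrinsic rhythm, so atrial pacing or another rhythm without P-waves could share the code. Sensing-test IEGMs are scheduled only at month 3 (CIP Table 7), and no stored IEGM is required for analyzer measurements (CIP 8.5.10). Counting all unresolved records as lost signal would be wrong.

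**SAP 5.6 plans no further subgroups.** The DX summaries are CIP commitments in their own right, and the SAP already makes DX-only and DF4-only tables for Plexa. The phrase in CIP 8.4.1 on lead type may mean only RA, RV and LV; the case for a group A split rests on the explicit DX-device item.

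**Conclusion.** The point holds in three parts. No adequacy rate for atrial sensing is tabulated in either group, although CIP 8.4.1, 8.4.2 and 8.5.11 call for it. In group A, RA amplitude is pooled over DX and conventional leads and DX use in HF-T QP devices is not reported, although CIP 8.4.1 promises both. Loss of atrial signal outside AF cannot be told apart from AF or from a measurement not done, and cannot lower the measured proportion, whereas the RV equivalent is reported.

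These are descriptive outputs. No primary or secondary hypothesis test changes, and a reader should not infer that the safety conclusions are affected. Nor do the documents show that any atrial signal was in fact lost. The size is unknown; 28/28 against 28/32 rests on assumed counts. SAP 19.2 says that only few DF-1 leads were implanted, and Plexa DX leads come only with DF-1 connectors, so group B numbers will be small.

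**What to change.** - **SAP 13.2:** set `fu3_perf_ra_sens` to Descriptive = Yes, split by DX versus conventional atrial lead.
- **SAP 21.2:** add RA sensing adequacy for Plexa DF-1 S DX, as n/N with an exact 95% CI.
- **SAP chapters 10, 11, 13 and 14:** split the group A RA amplitude tables by DX versus conventional lead, using `imp_rv_model` and `imp_dev_type`, and cross-tabulate DX use by ICD and CRT-D. Group A allows other RV leads, so confirm that the values of `imp_rv_model`, which the SAP abbreviates, also identify DX leads that are not Plexa.
- **Footnotes 26 and 39:** keep *No P-wave visible* as its own reported category. At month 3, where IEGMs are stored, subdivide it into AF, other rhythm or atrial pacing, and no atrial signal. At other visits, or without a usable IEGM, report it as unresolved and do not count it as lost signal.

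The cost is some table programming and review of a few stored IEGMs; no new patient procedure is needed. Intervals will be wide. With an assumed 10 DX patients all rated adequate, the exact 95% lower limit is 0.025^(1/10) = 69%.

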8.5 Methods

8.5.1 General

During the course of the study all clinical procedures are performed according to clinical routine. All parameters and measurements that are recorded within the study are described in this section and need to be documented on the electronic Case Report Forms (eCRF). The following eCRFs are used in this study.

- Enrollment Form
- Baseline Form
- Implantation Form
- Pre-Hospital Discharge Form
- MultiPole Pacing form (**group A** only)
- Plexa Lead Handling (**group B** only)
- 3-month follow-up form
- 6-month follow-up form
- Interim Intervention form
- Tachyarrhythmia episode form
- MRI AutoDetect form (**group A** only)
- Study termination Form
- Adverse Event Form
- Device Deficiency Form

For patients who are in both **groups A and B** all group-specific eCRFs need to be filled in.

All data have to be available for source data verification during monitoring visits of the sponsor. Patients have to consent to the use of their medical data in the patient file prior to enrollment by signing the informed consent form.

8.5.2 Patients' demographics and medical history

Demographic information including age, gender, height and weight will be collected for all subjects on the Baseline eCRF. Furthermore, information about the medical condition of the patient and the indications for CRT-D therapy or ICD therapy are interrogated. Further collected information is the medical history of the patient, current cardiovascular medication, NYHA class and ECG diagnostics within 3 months prior to implantation, if routinely available.

8.5.3 Implantation

The implantation of the Ilivia/Intica/Inlexa VR-T, VR-T DX, DR-T and HF-T QP as well as the implantation of the Plexa ICD lead is performed according to standard procedures as described in the technical manual of the respective device. Any lead delivery system can be used, however, BIOTRONIK accessories are recommended.

During implantation lead measurements via pacing sensing analyzer (PSA) (BIOTRONIK device recommended) will be conducted (see 8.5.10).

